7.10.1.4 Imputation of OAB Symptoms Onset Date

If the onset date of OAB symptoms is partially missing, the following rules will take effect:

15. Missing day, but month and year are present: the day will be imputed as the 15th day of the month.
16. Missing day and month, but year is present: the day and month will be imputed as 30 June of the year.
17. Missing year, but day and month are present: No imputations will occur, and the subject will be excluded from all summaries related to duration of OAB symptoms.
18. Missing day, month and year: No imputations will occur, and the subject will be excluded from all summaries related to duration of OAB symptoms.
19. If any such imputed date falls after the informed consent date, then the onset date will be taken as equal to the informed consent date.

7.10.2 Outliers

An outlier is defined as an observation for which the residual is more than three interquartile ranges above the 75th percentile or below the 25th percentile. Outliers will be identified based on diagnostics performed for the co-primary and secondary efficacy variables by using standardized residuals from ANCOVA model (Section 7.4.2). If outliers are present, then additional sensitivity analyses will be performed with the outliers excluded to assess their impact on the results.

7.10.3 Visit Windows

Subjects do not always adhere strictly to the visit timing in the protocol. Therefore, the designation of visits during the double-blind treatment period will be based on the day of

evaluation relative to the start of the double-blind treatment period (day of first dose of double-blind treatment in double-blind treatment period = Day 1 of double-blind treatment period) rather than the nominal visit recorded in the CRF.

To assign a measurement to a study visit during the double-blind treatment period, the first step consists of selecting all measurements falling within the double-blind treatment period as defined above. To further determine the study visit measurement, mutually exclusive relative day windows are used.

If a subject has more than one visit with a measurement included within a window, the assessment closest to the scheduled day will be used. In case of ties between observations located on different sides of the scheduled day, the later assessment will be used. In case of ties located on the same side of the scheduled day (i.e., more than one value for the same day), the mean of the values will be used for continuous variables and the worst value for categorical variables.

It should be noted that if more than one measurement for a parameter is recorded within the same visit window, the above conventions may not lead to the most conservative approach for the by-visit summaries of categorical or numerical variables. The worst individual categorical or numerical value within a visit window may not be identified as the value representative for the analysis visit due to the rules above. However, the worst individual categorical or numerical value will be accounted for in tables summarizing the worst individual categorical or numerical value reported during the double-blind treatment period. All individual values will be provided in a listing.

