--	--

	
Analysis on Secondary Endpoints The change from baseline to end of treatment for other secondary endpoints (excluding mean voided volume [MVV]) will be analyzed using a similar ANCOVA model as described above for mean number of micturitions per 24 hours. The change from baseline to end of treatment in MVV will be analyzed using the Stratified Rank ANCOVA and ANCOVA model as described above for mean number of incontinence episodes.
 
Safety: Safety analyses will be performed on the Safety Analysis Set (SAF) defined as all subjects who receive at least one dose of double-blind medication. Number and percentage of treatment-emergent adverse events reported during the double-blind period will be summarized by system organ class, preferred term, seriousness, severity, and relationship to treatment, overall and by treatment group.
 
Statistical differences in change from baseline to end of treatment in cognitive assessment will be tested using a paired sample Wilcoxon test.
 
Changes from baseline for PVR and laboratory assessments (biochemistry and hematology) will be summarized in tables by treatment group and visit.
 
Vital sign data will be analyzed separately based on the 3-day diary and the site assessment at each clinic visit. Change from baseline in vital sign variables will be analyzed using the same ANCOVA model as described for the analysis of change from baseline in mean number of micturitions per 24 hours. No p-values will be calculated.
 
ECGs will be performed at Screening (Visit 1), the placebo run-in period (Visit 2), Baseline (Visit 3), Week 4 (Visit 4), Week 8 (Visit 5), and Week 12/End of Treatment (Visit 6).
 
Interim Analysis: N/A

--	--

V. FLOW CHART AND SCHEDULE OF ASSESSMENTS

Figure 1 Flow Chart

[figure not shown]

Table 1 Schedule of Assessments

	Screening	Placebo Run-In	Treatment Period				Follow-up Phone Call
			1	2	3	4	
Visit	1	2	3	4	5	6	7
Day	-28	-14	1	28	56	84	112
Week	-4	-2	0/Baseline	4	8	12/EOT	16
Visit Windows (Days) ^a	+/- 10	+/- 3	+/- 3	+/- 7	+/- 7	+/- 7	+/- 3
Informed Consent/HIPAA	X						
Inclusion/Exclusion Criteria	X		X				
Medical History and OAB History	X						
Demographics	X						
Enter 2-week Placebo Run-in ^b		X					
Randomization ^c			X				
Physical Exam (including height ^d and weight)	X						X
Vital Signs – in office (includes pulse and blood pressure)	X	X	X	X	X	X	
Cough Provocation test (Females only)	X						
Serum chemistry, hematology & urinalysis ^e	X						X

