5.4.2 Patient Diary - Subject Measurement Vital Signs

During Visit 2 (Placebo Run-In), the Investigator should instruct the subject on how to perform and document in the electronic diary the self-measurement of BP and PR. The subject will have an opportunity to familiarize him/herself with the self-measurement of BP and PR and recording of the data.

Diaries for vital signs (measured at home) will be completed in both am and pm for 3 consecutive days prior to each visit: Baseline (Visit 3), Week 4 (Visit 4), Week 8 (Visit 5), and Week 12/End of Treatment (Visit 6).

Validated devices for measuring BP and PR will be provided to subjects along with detailed operating instructions. The Investigator should measure the circumference of the upper arm in order to give the subject the device with the correct cuff type (Adult: 25-35 cm; Adult Plus: 33-40 cm arm circumference).

At home, according to the “The ABCD’s of Blood Pressure Measurement” [American Heart Association, April 2012], the subject should rest for at least 5 minutes before taking the measurements. The subject should be quiet and relaxed, sitting in a chair with feet on the floor, legs should not be crossed, and arms should be bare and supported at heart level. The cuff should be put on according to the instructions of the Investigator. The subject should not move and should remain silent during the reading as moving and talking can affect the reading.

The subject should measure his/her BP and PR in triplicate during the 3 consecutive days prior to the next visit, on the arm chosen from the Screening measurements. Measurements should be taken after waking up in the morning and again in the evening. The subject should ensure that the morning measurements of vital signs are taken before breakfast and before study medication intake.

Three readings should be taken at every occasion, each about 2 minutes apart.

The subject should keep adequate records of the readings. Date, time, systolic and diastolic BP, and PR should be documented in the electronic diary. The subject should take care to have a 30 minute rest after exercise or smoking or intake of caffeine or alcohol, prior to taking a measurement.

An AE of tachycardia should be reported if the mean am or pm PR in the resting state from subject reported measurements at home over the last 3 diary days is >100 bpm.

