2 FLOW CHART AND VISIT SCHEDULE

[figure not shown]

Table 1 Schedule of Assessments

	Screening	Placebo Run-In	Treatment Period				Follow-Up Call
Visit	1	2	3	4	5	6	7
Day	-28	-14	1	30	60	90	120
Week	-4	-2	0/BL	4	8	12/EoT	16
Visit Window (Days) ^a	+/- 10	+/- 3	+/- 3	+/- 7	+/- 7	+/- 7	+/- 3
Informed Consent/HIPAA	X						
Inclusion/Exclusion Criteria	X		X				
Medical History and OAB History	X						
Demographics	X						
Enter 2-week Placebo Run-in ^b		X					
Randomization ^c			X				
Physical Exam (including height ^d and weight)	X					X	
Vital Signs (includes pulse and blood pressure)	X	X	X	X	X	X	
Cough Provocation test (Females Only)	X						
Serum Chemistry, hematology, & urinalysis	X					X	
██████████	████						
12-Lead ECG	X	X	X	X	X	X	
Ultrasound or Bladder Scan (PVR)	X					X	

Table continues on next page							
	Screening	Placebo Run-In	Treatment Period				Follow-Up Call
Medication History and OAB Medication History	X		X				
Visit	1	2	3	4	5	6	7
Day	-28	-14	1	30	60	90	120
Week	-4	-2	0/BL	4	8	12/EoT	16
Visit Window (Days) ^a	+/- 10	+/- 3	+/- 3	+/- 7	+/- 7	+/- 7	+/- 3
Clinical Assessment for Dose Increase				X	X		
Concomitant Medications Assessment	X	X	X	X	X	X	X
Adverse Event Assessment		X	X	X	X	X	X
Dispense Study Drug		X	X	X	X	X	
Drug Accountability			X	X	X	X	
Instruct Subject on 3-day Micturition Diary ^f	X	X	X	X	X	X	
Complete 3-day Micturition Diary including PPIUS ^g			X ^h	X ^h	X ^h	X ^h	
OAB-q			X	X	X	X	
Patient Perception of Bladder Condition Scores (PPBC)			X	X	X	X	
TS-VAS			X	X	X	X	
Montreal Cognitive Assessment Test (MoCA)			X			X	

Table continues on next page

	Screening	Placebo Run-In	Treatment Period				Follow-Up Call
University of Alabama Birmingham Life Space Assessment (UAB-LSA)			X	X	X	X	
Barthel ADL Assessment			X			X	
Vulnerable Elders Survey 13 (VES-13)			X			X	
Review Subject Diary ⁱ			X	X	X	X	

- a. After Visit 2 (Placebo Run-In), visit windows/study days will be calculated based on the Visit 3 (Baseline) visit date.
- b. Subjects must take at least 11 days, but no more than 17 days of placebo run-in medication.
- c. Randomization is to occur after confirming all eligibility criteria and after performing all other visit procedures at Visit 3.
- d. Height will only be assessed at the Screening Visit.
- e. [REDACTED]

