7.1.1 Last Observation Carried Forward (LOCF)

For the efficacy diary data the EoT value will be calculated as the average or the count of the valid diary measurements reported in the last 3 valid diary days of the analysis visit window prior to EoT. For subjects who withdraw before week 12, the last available post-baseline average of the diary data measurements will be carried forward as the EoT value (LOCF).

For the non-diary efficacy data and safety data, the EoT value will be the last measurement within the week 12 visit day windows. For subjects who withdraw before week 12 the last measurement within the analysis visit window of the last available post-baseline visit will be carried forward as the EoT value (LOCF).

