7.10.3.1 Analysis Visit Windows for Efficacy and Safety Variables

All the efficacy and safety assessments for a treatment period will be allocated based on the tables below.

Efficacy:

Analysis visit	Target day	Actual assessment day
Screening	Day -28	-38 to -18
Placebo Run-In	Day -14	-17 to 0
Baseline	Day 1	Day 1 ^a
Week 4	Day 30	15-42
Week 8	Day 60	43-70
Week 12/End of Treatment	Day 90	71-98
Follow Up Phone Call	Day 120	EOT+14

After Placebo Run-In, visit windows/study days will be calculated based on the Baseline (Visit 3) date.

Safety:

Analysis visit	Target day	Actual assessment day
Screening	Day -28	-38 to -18
Placebo Run-In	Day -14	-17 to 0
Baseline	Day 1	Day 1 ^a
Week 4	Day 30	2-45
Week 8	Day 60	46-75
Week 12/End of Treatment	Day 90	76-97
Follow Up Phone Call	Day 120	EOT+14

1. After Placebo Run-In, visit windows/study days will be calculated based on the Baseline (Visit 3) date.

For efficacy variables recorded in the 3-day micturition diary, the following rules will apply:

1. As micturition diary data are to be recorded from midnight 3 days prior to a visit to midnight 1 day prior to a visit, micturition diary records which have the same date as a visit date should be excluded from the analysis. Non-micturition questionnaire assessment dates will be compared to the eDiary dates and used to flag which diary records should be excluded.
2. Any diary days which are > 7 days after the last dose of double-blind treatment will not be included in the analysis.
3. Average values or number of episodes for count data will only be calculated if at least 2 valid diary days are available within the specified window. In the case that only 1 valid diary day is available, then no value will be calculated.
4. If there are more than 3 valid diary days available for a visit, the average will be based on the last 3 days prior to the scheduled visit.
5. Duplicate records (same time and episode characteristics) per day during the 3-day micturition diary period will be excluded.

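### The SAP's visit target days (30/60/90/120) contradict the protocol's (28/56/84/112), and its safety windows follow one calendar while its efficacy windows follow the other

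*SAP*

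**What the plan says.** - **Protocol schedule.** Protocol Table 1 (Schedule of Assessments) has the row "Day -28 -14 1 28 56 84 112", with ±7 days allowed at Visits 4, 5 and 6.
- **SAP schedule.** SAP section 2, Table 1, has "Day -28 -14 1 30 60 90 120" for the same visits, also with ±7 days at Visits 4 to 6.
- **SAP windows.** SAP 7.10.3.1 gives one table for efficacy and one for safety, both with targets 30, 60, 90 and 120. The efficacy table includes "Week 12/End of Treatment Day 90 71-98". The safety table includes "Week 8 Day 60 46-75", and its Week 12 row covers Days 76-97.
- **Selection rule.** SAP 7.10.3 assigns measurements by actual study day, not by nominal visit. If several visits fall in one window, "the assessment closest to the scheduled day will be used".
- **End of treatment.** For non-diary efficacy and safety data, SAP 7.1.1 says "the EoT value will be the last measurement within the week 12 visit day windows".
- **Home blood pressure.** Protocol 5.4.2 has subjects measure it "in triplicate during the 3 consecutive days prior to the next visit". SAP 7.5.3 drops the first reading of each set and averages the other two over the 3-day diary.

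**The concern.** Visits take place on the protocol's calendar, but the SAP labels data on a calendar that drifts 2 days later per visit. Only one of its two window tables shares that drift. A programmer following the SAP literally could therefore give efficacy and safety data from one visit different labels, choose the less timely of two assessments, and build a Week 12 home blood pressure mean on fewer than three days.

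What is at stake is the by-visit summaries of questionnaires, vital signs and ECG, and the SAP 7.5.3 counts of blood pressure and pulse increases on two consecutive visits, which depend on visit labels. Home measurements were added by Amendment 2 to give more safety data on hypertension, so their derivation should be unambiguous.

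**Working it through.** **1. Which calendar each table uses.** Take cut-points as midpoints between adjacent targets.

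| Targets | Midpoints | Window table that matches |
|---|---|---|
| 28/56/84 (protocol) | (28+56)/2 = 42; (56+84)/2 = 70 | Efficacy: 15-42, 43-70, 71-98 |
| 30/60/90 (SAP) | (30+60)/2 = 45; (60+90)/2 = 75 | Safety: 2-45, 46-75, 76-97 (90+7 = 97) |

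The efficacy windows are 28 days wide with centres 28.5, 56.5 and 84.5, so the targets printed beside them do not fit. The SAP's exposure categories (7.3.1) also break at 28, 56 and 84 days. The target offsets from the protocol are 30−28 = 2, 60−56 = 4, 90−84 = 6 and 120−112 = 8 days.

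**2. Days labelled differently.**

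| Day | Efficacy label | Safety label |
|---|---|---|
| 43-45 | Week 8 | Week 4 |
| 71-75 | Week 12 | Week 8 |
| 98 | Week 12 | none |

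Days 2-14 also differ (no efficacy label, Week 4 for safety), but that comes from the choice of lower limit, not from the calendar.

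The permitted visit days are 28±7 = 21-35, 56±7 = 49-63 and 84±7 = 77-91. Each range lies inside one window of each table, so the labels above differ only for out-of-window or early-withdrawal visits. Example: a subject has a Week 8 visit on Day 56 and withdraws at a visit on Day 73. The Day 73 questionnaires become Week 12. The Day 73 office vital signs fall in the Week 8 safety window and lose to Day 56 (|73−60| = 13 against |56−60| = 4).

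**3. Closest-day rule.** This applies only with two or more assessments in a window.
- Days 84 and 95: target 84 gives distances 0 and 11 and selects Day 84. Target 90 gives 6 and 5 and selects Day 95.
- Days 56 and 63: target 56 gives 0 and 7 and selects Day 56. Target 60 gives 4 and 3 and selects Day 63.

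**4. Home blood pressure, if each diary day is windowed separately.** The diary days are visit day −3 to −1, and the safety cut is at Day 75.
- Visit on Day 77: Days 74 and 75 go to Week 8 and Day 76 to Week 12. One of three days is left.
- Visit on Day 78: Day 75 goes to Week 8 and Days 76 and 77 to Week 12. Two of three are left.
- Visits on Days 79-91: the earliest diary day is 79−3 = 76, so all three stay in Week 12.

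That is 2 of 15 permitted days. The micturition diary for the same dates stays whole in its 71-98 window.

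Sensitivity: SAP 7.10.3 counts from first dose, while the table note and the protocol count from the Baseline visit. If the first dose falls one day after Baseline, a Day 77 visit sends all three days to Week 8, Days 78 and 79 split, and a Week 8 visit on Day 49 also splits.

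**5. Windows on the protocol's calendar.** With safety windows 2-42, 43-70 and 71-98, diary days for permitted visits run from 21−3 = 18 to 35−1 = 34, from 46 to 62, and from 74 to 90. All lie inside their windows, and still do if each is shifted back one day. Nothing splits.

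**The case against.** The strongest reply is that the protocol's visit ranges fit inside the SAP windows, so the wrong targets do nothing for a subject seen on schedule. That stands. Two assessments share a window only when one is unscheduled or out of window; Day 95, for instance, is outside 77-91. After Visit 6 the protocol schedules only a phone call for medication and adverse events.

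A second reply is that SAP 7.5.3 treats the 3-day diary as one average and that 7.10.3 speaks of visits with a measurement. Windowing each day separately would also make the closest-day rule keep one day at every visit, which is hardly intended. This is a fair reading, and it removes the split. But the SAP does not state it, does not say which day would place the unit, and sets no minimum number of days for home readings, as it does for the micturition diary.

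Three stronger inferences are tempting and not supported:
- *Week 12 questionnaires and vital signs may freely come from after treatment.* SAP 7.10.3 first restricts to measurements within the double-blind period. The end of that period is poorly defined, but a restriction exists.
- *SAP 7.1.1 and 7.10.3 flatly contradict each other.* One can govern the end-of-treatment value and the other by-visit values; SAP 7.4.2, 7.4.3 and 7.4.5 list Week 12 and EoT separately. The shared Week 12/End of Treatment row only blurs this.
- *About 13% of subjects lose home readings.* 2/15 = 13% is a share of permitted days. It becomes a share of subjects only if visits spread evenly over the window, which nothing in the documents shows.

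**Conclusion.** A minor but genuine inconsistency between current protocol text and current SAP text, and within the SAP itself. It mislabels out-of-window and early-withdrawal assessments on Days 43-45 and 71-75, leaves Day 98 without a safety label, and shifts the closest-day reference by 2, 4 or 6 days whenever a window holds an extra assessment. The number of subjects affected cannot be derived from the documents. The loss of home blood pressure days at Week 12 visits on Days 77 and 78 is conditional on day-by-day windowing.

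The co-primary endpoints are not touched: they use the last 3 valid diary days, and no permitted visit splits a micturition diary. Office assessments at in-window visits carry the right label in both tables. The closest-day rule need not affect end-of-treatment values of non-diary data, which take the last measurement.

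**What to change.** 1. Set the targets to Days 28, 56, 84 and 112 in SAP Table 1 and in both tables of SAP 7.10.3.1, matching the schedule under which visits are made.
2. Set the safety windows to 2-42, 43-70 and 71-98. The efficacy windows need no change.
3. In SAP 7.5.3 or 7.10.3, state that the 3-day home blood pressure diary is windowed as one unit, and which day places it.
4. State that the closest assessment governs by-visit values and the last assessment governs EoT.

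The cost is a SAP revision before database hard lock and small changes to derivation code. Sites, data collection and sample size are unaffected.

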7.10.3.1 Analysis Visit Windows for Efficacy and Safety Variables

All the efficacy and safety assessments for a treatment period will be allocated based on the tables below.

Efficacy:

Analysis visit	Target day	Actual assessment day
Screening	Day -28	-38 to -18
Placebo Run-In	Day -14	-17 to 0
Baseline	Day 1	Day 1 ^a
Week 4	Day 30	15-42
Week 8	Day 60	43-70
Week 12/End of Treatment	Day 90	71-98
Follow Up Phone Call	Day 120	EOT+14

After Placebo Run-In, visit windows/study days will be calculated based on the Baseline (Visit 3) date.

Safety:

Analysis visit	Target day	Actual assessment day
Screening	Day -28	-38 to -18
Placebo Run-In	Day -14	-17 to 0
Baseline	Day 1	Day 1 ^a
Week 4	Day 30	2-45
Week 8	Day 60	46-75
Week 12/End of Treatment	Day 90	76-97
Follow Up Phone Call	Day 120	EOT+14

1. After Placebo Run-In, visit windows/study days will be calculated based on the Baseline (Visit 3) date.

For efficacy variables recorded in the 3-day micturition diary, the following rules will apply:

1. As micturition diary data are to be recorded from midnight 3 days prior to a visit to midnight 1 day prior to a visit, micturition diary records which have the same date as a visit date should be excluded from the analysis. Non-micturition questionnaire assessment dates will be compared to the eDiary dates and used to flag which diary records should be excluded.
2. Any diary days which are > 7 days after the last dose of double-blind treatment will not be included in the analysis.
3. Average values or number of episodes for count data will only be calculated if at least 2 valid diary days are available within the specified window. In the case that only 1 valid diary day is available, then no value will be calculated.
4. If there are more than 3 valid diary days available for a visit, the average will be based on the last 3 days prior to the scheduled visit.
5. Duplicate records (same time and episode characteristics) per day during the 3-day micturition diary period will be excluded.

8 DOCUMENT REVISION HISTORY

Version	Date	Changes	Comment/rationale for change
1.00	03-SEP-2014	NA	Document Initialized
2.00	12-FEB-2016	YES	Changes in Protocol Amendment 2
3.00	08-SEP-2017	YES	Changes per sponsor's comments

10 APPENDICES

10.1 Appendix 1: Adverse Events of Possible Hepatic Origin

MedDRA Hepatic Disorders SMQ

Congenital, familial, neonatal and genetic disorders of the liver (SMQ)

- Accessory liver lobe
- Alagille syndrome
- Cerebrohepatorenal syndrome
- Congenital absence of bile ducts
- Congenital cystic disease of liver
- Congenital hepatic fibrosis
- Congenital hepatobiliary anomaly
- Congenital hepatomegaly
- Cystic fibrosis hepatic disease
- Dilatation intrahepatic duct congenital
- Glycogen storage disease type I
- Glycogen storage disease type III
- Glycogen storage disease type IV
- Glycogen storage disease type VI
- Hepatitis neonatal
- Hepatocellular damage neonatal
- Hepato-lenticular degeneration
- Hepatosplenomegaly neonatal
- Hereditary haemochromatosis
- Neonatal cholestasis
- Neonatal hepatomegaly
- Polycystic liver disease
- Porphyria acute
- Hyperbilirubinaemia neonatal
- Jaundice neonatal
- Kernicterus
- Porphyria non-acute

Drug related hepatic disorders - comprehensive search (SMQ)

Cholestasis and jaundice of hepatic origin (SMQ)

- Bilirubin excretion disorder
- Cholaemia
- Cholestasis
- Cholestatic liver injury
- Cholestatic pruritus
- Drug-induced liver injury
- Hepatitis cholestatic
- Hyperbilirubinaemia
- Icterus index increased
- Jaundice

Jaundice cholestatic
Jaundice hepatocellular
Mixed liver injury
Ocular icterus
Deficiency of bile secretion
Yellow skin
Drug related hepatic disorders - severe events only (SMQ)
Hepatic failure, fibrosis and cirrhosis and other liver damage-related conditions (SMQ)
Acute hepatic failure
Acute yellow liver atrophy
Ascites
Asterixis
Bacterascites
Biliary cirrhosis
Biliary cirrhosis primary
Biliary fibrosis
Cholestatic liver injury
Chronic hepatic failure
Coma hepatic
Cryptogenic cirrhosis
Diabetic hepatopathy
Drug-induced liver injury
Duodenal varices
Gallbladder varices
Gastric varices
Gastric varices haemorrhage
Hepatectomy
Hepatic atrophy
Hepatic calcification
Hepatic cirrhosis
Hepatic encephalopathy
Hepatic encephalopathy prophylaxis
Hepatic failure
Hepatic fibrosis
Hepatic hydrothorax
Hepatic infiltration eosinophilic
Hepatic lesion
Hepatic necrosis
Hepatic steatosis
Hepatitis fulminant
Hepatobiliary disease
Hepatocellular foamy cell syndrome

Hepatocellular injury
Hepatopulmonary syndrome
Hepatorenal failure
Hepatorenal syndrome
Hepatotoxicity
Intestinal varices
Liver and small intestine transplant
Liver disorder
Liver injury
Liver operation
Liver transplant
Lupoid hepatic cirrhosis
Mixed liver injury
Nodular regenerative hyperplasia
Non-alcoholic steatohepatitis
Oedema due to hepatic disease
Oesophageal varices haemorrhage
Peripancreatic varices
Portal hypertension
Portal hypertensive enteropathy
Portal hypertensive gastropathy
Portal triaditis
Portal vein dilatation
Portopulmonary hypertension
Renal and liver transplant
Retrograde portal vein flow
Reye's syndrome
Reynold's syndrome
Splenic varices
Splenic varices haemorrhage
Subacute hepatic failure
Varices oesophageal
Varicose veins of abdominal wall
Anorectal varices
Anorectal varices haemorrhage
Intrahepatic portal hepatic venous fistula
Peritoneovenous shunt
Portal shunt
Small-for-size liver syndrome
Spider naevus
Hepatitis, non-infectious (SMQ)
Acute graft versus host disease in liver
Allergic hepatitis

- Autoimmune hepatitis
- Chronic graft versus host disease in liver
- Chronic hepatitis
- Graft versus host disease in liver
- Hepatitis
- Hepatitis acute
- Hepatitis cholestatic
- Hepatitis chronic active
- Hepatitis chronic persistent
- Hepatitis fulminant
- Hepatitis toxic
- Ischaemic hepatitis
- Lupus hepatitis
- Non-alcoholic steatohepatitis
- Radiation hepatitis
- Granulomatous liver disease
- Liver sarcoidosis
- Liver neoplasms, benign (incl cysts and polyps) (SMQ)
 - Benign hepatic neoplasm
 - Focal nodular hyperplasia
 - Haemangioma of liver
 - Haemorrhagic hepatic cyst
 - Hepatic adenoma
 - Hepatic cyst
 - Hepatic cyst ruptured
 - Hepatic haemangioma rupture
- Liver neoplasms, malignant and unspecified (SMQ)
 - Liver malignant tumours (SMQ)
 - Hepatic angiosarcoma
 - Hepatic cancer metastatic
 - Hepatic cancer stage I
 - Hepatic cancer stage II
 - Hepatic cancer stage III
 - Hepatic cancer stage IV
 - Hepatoblastoma
 - Hepatoblastoma recurrent
 - Hepatocellular carcinoma
 - Mixed hepatocellular cholangiocarcinoma
 - Liver tumours of unspecified malignancy (SMQ)
 - Hepatic neoplasm
 - Hepatobiliary neoplasm
- Liver related investigations, signs and symptoms (SMQ)
 - Alanine aminotransferase abnormal

Alanine aminotransferase increased
Ammonia abnormal
Ammonia increased
Ascites
Aspartate aminotransferase abnormal
Aspartate aminotransferase increased
Bacterascites
Bile output abnormal
Bile output decreased
Bilirubin conjugated abnormal
Bilirubin conjugated increased
Biopsy liver abnormal
Blood bilirubin abnormal
Blood bilirubin increased
Blood bilirubin unconjugated increased
Bromosulphthalein test abnormal
Child-Pugh-Turcotte score increased
Foetor hepaticus
Galactose elimination capacity test abnormal
Galactose elimination capacity test decreased
Gamma-glutamyltransferase abnormal
Gamma-glutamyltransferase increased
Guanase increased
Hepaplastin abnormal
Hepaplastin decreased
Hepatic artery flow decreased
Hepatic congestion
Hepatic enzyme abnormal
Hepatic enzyme decreased
Hepatic enzyme increased
Hepatic function abnormal
Hepatic hydrothorax
Hepatic mass
Hepatic pain
Hepatic sequestration
Hepatic vascular resistance increased
Hepatobiliary scan abnormal
Hepatomegaly
Hepatosplenomegaly
Hyperammonaemia
Hyperbilirubinaemia
Hypercholia
Hypertransaminasaemia

Kayser-Fleischer ring
Liver function test abnormal
Liver induration
Liver palpable subcostal
Liver scan abnormal
Liver tenderness
Mitochondrial aspartate aminotransferase increased
Molar ratio of total branched-chain amino acid to tyrosine
Oedema due to hepatic disease
Perihepatic discomfort
Retrograde portal vein flow
Total bile acids increased
Transaminases abnormal
Transaminases increased
Ultrasound liver abnormal
Urine bilirubin increased
X-ray hepatobiliary abnormal
5'nucleotidase increased
Blood alkaline phosphatase abnormal
Blood alkaline phosphatase increased
Blood cholinesterase abnormal
Blood cholinesterase decreased
Deficiency of bile secretion
Glutamate dehydrogenase increased
Haemorrhagic ascites
Hypoalbuminaemia
Leucine aminopeptidase increased
Periportal oedema
Peritoneal fluid protein abnormal
Peritoneal fluid protein decreased
Peritoneal fluid protein increased
Pneumobilia
Portal vein flow decreased
Portal vein pressure increased
Retinol binding protein decreased
Urobilinogen urine decreased
Urobilinogen urine increased
Liver-related coagulation and bleeding disturbances (SMQ)
Antithrombin III decreased
Blood fibrinogen abnormal
Blood fibrinogen decreased
Blood thrombin abnormal
Blood thrombin decreased

Blood thromboplastin abnormal
Blood thromboplastin decreased
Coagulation factor decreased
Coagulation factor IX level abnormal
Coagulation factor IX level decreased
Coagulation factor V level abnormal
Coagulation factor V level decreased
Coagulation factor VII level abnormal
Coagulation factor VII level decreased
Coagulation factor X level abnormal
Coagulation factor X level decreased
Hypocoagulable state
Hypofibrinogenaemia
Hypoprothrombinaemia
Hypothrombinaemia
Hypothromboplastinaemia
International normalised ratio abnormal
International normalised ratio increased
Protein C decreased
Protein S abnormal
Protein S decreased
Prothrombin level abnormal
Prothrombin level decreased
Prothrombin time abnormal
Prothrombin time prolonged
Prothrombin time ratio abnormal
Prothrombin time ratio increased
Thrombin time abnormal
Thrombin time prolonged

Hepatic disorders specifically reported as alcohol-related (SMQ)

Alcoholic liver disease

Cirrhosis alcoholic

Fatty liver alcoholic

Hepatitis alcoholic

Zieve syndrome

Liver infections (SMQ)

Acute hepatitis B

Acute hepatitis C

Adenoviral hepatitis

Asymptomatic viral hepatitis

Chronic hepatitis B

Chronic hepatitis C

Congenital hepatitis B infection

Cytomegalovirus hepatitis
HBV-DNA polymerase increased
Hepatic amoebiasis
Hepatic candidiasis
Hepatic cyst infection
Hepatic echinococcosis
Hepatic infection
Hepatic infection bacterial
Hepatic infection fungal
Hepatic infection helminthic
Hepatitis A
Hepatitis A antibody abnormal
Hepatitis A antibody positive
Hepatitis A antigen positive
Hepatitis A virus test positive
Hepatitis B
Hepatitis B antibody abnormal
Hepatitis B antibody positive
Hepatitis B core antibody positive
Hepatitis B core antigen positive
Hepatitis B DNA assay positive
Hepatitis B DNA increased
Hepatitis B e antibody positive
Hepatitis B e antigen positive
Hepatitis B surface antibody positive
Hepatitis B surface antigen positive
Hepatitis B virus test positive
Hepatitis C
Hepatitis C antibody positive
Hepatitis C RNA increased
Hepatitis C RNA positive
Hepatitis C virus test positive
Hepatitis D
Hepatitis D antibody positive
Hepatitis D antigen positive
Hepatitis D RNA positive
Hepatitis D virus test positive
Hepatitis E
Hepatitis E antibody abnormal
Hepatitis E antibody positive
Hepatitis E antigen positive
Hepatitis E virus test positive
Hepatitis F

Hepatitis G
Hepatitis H
Hepatitis infectious
Hepatitis infectious mononucleosis
Hepatitis mumps
Hepatitis non-A non-B
Hepatitis non-A non-B non-C
Hepatitis post transfusion
Hepatitis syphilitic
Hepatitis toxoplasmal
Hepatitis viral
Hepatitis viral test positive
Hepatobiliary infection
Hepatosplenic candidiasis
Herpes simplex hepatitis
Liver abscess
Schistosomiasis liver
Viral hepatitis carrier
Withdrawal hepatitis
Gianotti-Crosti syndrome
Portal pyaemia
Weil's disease
Pregnancy-related hepatic disorders (SMQ)
Acute fatty liver of pregnancy
Cholestasis of pregnancy

